4.0 Drug Regimens

Subjects will be randomized to either oral udenafil or matching placebo. Subjects will take udenafil 87.5 mg or matching placebo twice a day. Duration of study drug administration will be six months. Study drug may be temporarily discontinued for up to 2 weeks for side effects. Study drug may be resumed on resolution of symptoms or side effects if considered safe in the judgment of the investigators and the subject's primary physician and with consent of subject.

Study drug will be permanently discontinued if deemed necessary by the study investigator or primary physician either due to side-effects or due to need for open-label drug administration of a PDE5 inhibitor.

5.0 Study Procedures

Study procedures will be performed as outlined in **Error! Reference source not found.**. In-clinic procedures associated with the first dose of study drug at Visit 1 are outlined in Table 1.

CONFIDENTIAL

Table 1 Schedule of Measurements/Events

Visit Number	1	TC1	TC2	2	TC3-5	3	TC6-7	4	TC8-10
Time point	Screening/ Baseline Day 0	Day 1	Week 1	Week2	Weeks 3, 4, 8	Week 13	Week 17, 21	Week 26	Week 30, 34, 39
Visit Window(s)			± 3 days	± 3 days	± 3 days	±10 days	± 3 days	±10 days	± 10 days
Type of Visit(s)	In-Person	Call	Call	In- Person	Call	In- Person	Call	In- Person	Call
Informed Consent/Assent	X								
Subject ID# assigned	X								
Inclusion/Exclusion Criteria	X								
Physical Measurements	X								
Medical history	X								
Demographics/expanded demo	X								
Prior/Concomitant Meds	X		X	X	X	X	X	X	
EndoPAT®	X								X
Serum or urine pregnancy test^a	X			X		X		X	
Clinical Laboratory tests (creatinine, ALT, AST)	X								X
Biomarker (BNP) sample	X								X
Genetic repository sample (optional)	X ^a								X ^b
Echocardiogram	X								X
Exercise test	X ^c								X ^c
Randomization	X								
Dispense Study Drug	X			X		X			
Resting BP and HR	X			X		X		X	
Administer first dose of study drug (see Additional Procedures and Measurements in Table 2)	X								
Peds QL generic and cardiac modules; PCQLI; HAES	X								X
Drug Accountability	X		X	X	X	X	X	X	
Pregnancy counseling (if applicable)	X		X	X	X	X	X	X	
Adverse events assessment	X	X	X	X	X	X	X	X	X ^a
Morisky Scale (MMAS)			X		X		X		
Schedule/Confirm next visit	X	X	X	X	X	X	X	X	

^aas applicable^bas applicable if missed at baseline visit^cBaseline visit: If failed 1st exercise test, do NOT randomize; At baseline and Week 26 visits, at Site Investigator's discretion, exercise test may be repeated w/in 14 days -- If a second exercise test needed, you MUST perform urine (or blood) pregnancy test for eligibility (if applicable).

CONFIDENTIAL

Table 1 Schedule of Assessments at Visit 1

Procedure	Time From Administration of First Dose of Study Drug			
	< 1 Hour Prior to Dose	0 Hour	2 Hours (± 30 Minutes)	4 Hours (± 30 Minutes)
Resting vital signs ^a	X			X ^b
Administer first dose of study drug		X		
Vital signs immediately before and following a 6-minute self-limited walk			X	
Pharmacokinetic blood sample immediately after 6-minute walk			X	
Record adverse events		X	X	X
Dispense study drug for home administration				X
Discharge from clinic				X

a Includes blood pressure and heart rate.

b Before discharge from the clinic.

6.0 Statistics

All statistical tests will be at the 0.05 alpha level, 2-tailed, unless stated otherwise. Probabilities will be rounded to 4 decimal places before assigning statistical significance.

Descriptive statistics for categorical endpoints will include the number and percent of subjects in each treatment group and category. Quantitative endpoints will be summarized for each treatment group with the mean, median, standard deviation, minimum value, and maximum value.

Individual subject data will be presented in data listings, which will include normal reference ranges when appropriate.

6.1 Analysis Populations

Three analysis populations will be defined:

- Intent-to-treat (ITT) Population: The population will include all randomized subjects and will be the primary population for efficacy analyses. Treatment assignments will be analyzed according to the randomized treatment assignment.
- Safety Population: The population will include all subjects who take at least one dose of randomized study drug and will be the primary population for safety analyses. If the wrong study drug is administered (e.g., subject is randomized to udenafil but receives placebo), treatment assignments will be analyzed according to the actual study drug received.
- Per Protocol Population: The population will include all subjects in the Safety Population who meet all entry criteria, or if criteria were not met, were granted a waiver by the Sponsor. Subjects with major protocol deviations will be excluded

CONFIDENTIAL

(including subjects who receive the wrong study drug). The Per Protocol Population will be used for sensitivity analyses of the primary efficacy endpoint.

6.2 Accountability and Protocol Deviations

Screening failures (i.e., subjects who were not randomized) will be summarized by the number and percentage of failures for each primary reason.

The number and percent of subjects who are randomized, treated with randomized study drug, prematurely discontinue, and complete the study will be summarized by treatment group. The number and percent of subjects will be summarized by treatment group for each reason for premature discontinuation. For subjects who complete the study, the number of subjects who continue into the extension study will be summarized.

The number and percent of enrolled subjects will be summarized by study site.

The number of subjects included in each analysis population will be summarized by treatment group.

Major protocol deviations will be identified prior to breaking the blind. Deviations may include, but are not limited to, departure from inclusion/exclusion criteria, received the wrong study drug; failure to perform the required assessments at specified time points; and scheduling of visits not in accordance with specifications.

6.3 Demographic and Baseline Characteristics

Demographic (e.g., age, sex, and race) and baseline characteristics will be summarized descriptively for the Safety and ITT Populations. Summaries will be provided for all subjects and for each treatment group.

Medical and surgical history/physical findings will be classified by system organ class and preferred term using the Medical Dictionary for Regulatory Activities (MedDRA). The number and percentage of subjects with abnormalities in medical and surgical histories in each system organ class and preferred term will be summarized for all subjects and by treatment group for the Safety Population.

6.4 Efficacy Analyses

6.4.1 Primary Efficacy Endpoint (Aerobic Exercise Performance)

The treatment group difference for change in aerobic exercise performance (as measured by VO₂ at maximum exercise effort [maximal VO₂]) from baseline to Visit 4 will be assessed with an analysis of covariance (ANCOVA) with fixed factors for ventricular morphology (single left versus single right or mixed) and treatment group with a continuous covariate of baseline maximal VO₂.

CONFIDENTIAL

Sensitivity analyses will include:

- Primary efficacy analysis performed for the Per Protocol Population
- ANCOVA model to assess treatment group differences in ranked changes of maximal VO₂ for the ITT and Per Protocol Populations.

6.4.2 Secondary Efficacy Endpoints

Secondary efficacy endpoints include change from baseline to Visit 4 (Week 26) in:

- Exercise capacity
 - Minute oxygen consumption at the ventilator anaerobic threshold (VAT)
 - Ventilatory equivalents of carbon dioxide (VE/VCO₂) at VAT
 - Respiratory rate and minute ventilation at peak exercise
 - Maximal work rate
 - Work rate at the VAT
- Ventricular performance
 - Myocardial performance index (MPI) determined by velocities obtained from blood pool Doppler assessment of the inflow and outflow tract of the dominant ventricle. It is the primary performance endpoint of the echocardiogram.
 - Ventricular cavity size, eccentricity, and mass (based on echocardiogram)
 - Systolic function estimate using mean dP/dt during isovolumetric contraction (dP/dt_{ic}) and peak systolic annular velocity (S') on tissue Doppler
 - Qualitative and quantitative estimate of atrioventricular valve insufficiency
- Endothelial function: log-transformed reactive hyperemia index (lnRHI), as measured by pulse amplitude tonometry (PAT) testing using the EndoPAT® device
- Natural logarithm transformation of BNP
- Functional health status as measured by the full scale PedsQL
 - Physical functioning score

CONFIDENTIAL

- Psychosocial functioning score
- Cardiac-specific quality-of-life score
- Pediatric Cardiac Quality of Life Inventory (PCQLI) score

Each secondary efficacy endpoint will be summarized descriptively by treatment group.

Treatment group differences for endpoints associated with the PedsQL and PCQLI will be assessed with Friedman's test using ventricular morphology (single left versus single right or mixed) as the stratification factor. The treatment group difference for the qualitative estimate of atrioventricular valve insufficiency will be assessed with a Cochran-Mantel-Haenszel test using ventricular morphology (single left versus single right or mixed) as the stratification factor.

The remaining secondary efficacy endpoints will be analyzed with the ANCOVA model with fixed factors for ventricular morphology (single left versus single right or mixed) and treatment group with a covariate for the baseline value.

6.4.3 Missing Data

The following imputation method will be used for the primary analysis of the primary outcome:

- Subjects who have died or have dropped out of the study with unknown vital status will be assigned a maximal VO₂ of zero at Visit 4.
- Subjects who are known to be alive, but who discontinued from the study (and are missing maximal VO₂ at Visit 4) will be assigned the latest value available (e.g., value from end of study visit if available, and from baseline visit otherwise).
- Subjects who complete Visit 4, but are physically unable to reach maximum effort in cardiopulmonary exercise testing after two attempts, will be assigned their baseline value (i.e., zero change).

Two additional analyses to assess the impact of missing data will be conducted as follows:

- Subjects with missing maximal VO₂ at Visit 4 will be assigned a maximal VO₂ of zero
- Subjects with missing maximal VO₂ at Visit 4 will be excluded from analysis (i.e., observed cases analysis).

Missing item scores for rating scales will be imputed according to published methodology for the scale. Otherwise, missing data will not be estimated for secondary efficacy endpoints.

CONFIDENTIAL

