The VO_2 at VAT measures the level of oxygen consumption at which one changes from aerobic to anaerobic activity, a clinically relevant level of exertion that is typical of what is encountered in routine volitional activity. For reasons discussed in detail in Section 11.4.7, VO_2 at VAT may be more appropriate than maximal VO_2 as an outcome measure for those with a single ventricle circulation. As is true for maximal VO_2 , measurements of VO_2 at VAT also correlate with functional outcome. For this clinical study, VO_2 at VAT was chosen as a secondary exercise measure due to the technical challenge associated with obtaining measurements of the endpoint. Determination of VO_2 at VAT depends on each participant maintaining a consistent respiratory pattern over the duration of their exercise test. This is generally achievable by older adolescents and adults, but it may be less reliable in younger adolescents. However, as discussed in Section 11.4.7, our understanding of Fontan exercise physiology has evolved since the inception of this study and, even with the technical challenges, the importance of VO_2 at VAT as a critical surrogate endpoint for those who have undergone Fontan has become apparent.

Echocardiography is routinely and universally used to evaluate ventricular performance in serial follow-up of Fontan patients, a population known to have significant abnormalities in both ventricular systolic and diastolic function (Sano 1989; Frommelt 1991; Akagi 1993; Cheung 2000; Kaneko 2012). Animal studies have suggested that PDE-5 inhibitors may mitigate adverse remodeling in stressed myocardium, and previous single dose trials and pilot studies in those with a Fontan circulation have suggested an improvement in ventricular performance in response to treatment (Goldberg 2012; Tunks 2014; Van De Brueaene 2014;

[Goldberg 2017](#); [Garcia 2018](#)). Given the importance of ventricular performance in the long-term health of those with all forms of heart disease, an improvement in this aspect of physiology would be of significant value across the population. The MPI is a measure of systolic and diastolic function that indexes isovolumetric relaxation and contraction times to the ventricular ejection time; a smaller number suggests more efficient contraction and relaxation. An improvement in MPI would be of benefit in this population, one with well documented abnormalities in systolic and diastolic function.

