11.4.1.3 VO₂ at Ventilatory Anaerobic Threshold

The udenafil group had a mean increase from baseline to Week 26 in VO₂ at VAT (29.65 mL/min) as compared to a mean decrease in the placebo group (-8.01 mL/min). The least squares mean treatment group difference for change from baseline to Week 26 in VO₂ at VAT was 41.58 mL/min (p=0.023). When standardized by each subject's body weight, the least squares mean treatment group difference was 0.78 mL/kg/min (p=0.012). The analysis of change from baseline to Week 26 in VO₂ at VAT (expressed as mL/min and mL/kg/min) is summarized in [Table 15](#).

Table 15: Change in VO₂ at VAT Between Week 26 and Baseline Visits Using Last Observation Carried Forward (ITT Population)

	Udenafil (N=200)	Placebo (N=200)	Difference LS Mean (SE)	p-value
VO₂ at VAT (mL/min)				
Baseline	n=170	n=181		
Mean (SD)	1039.41 (300.779)	1020.50 (279.683)	19.06 (30.963)	0.539 ^a
Week 26	n=185	n=191		
Mean (SD)	1059.03 (291.999)	1014.45 (277.017)	56.72 (30.595)	0.065 ^a
Difference, Week 26 minus baseline	n=170	n=181		
Mean (SD)	29.65 (177.023)	-8.01 (183.031)	41.58 (18.224)	0.023 ^b
Median	20.00	0.00		
VO₂ at VAT (mL/kg/min)				
Baseline	n=170	n=181		
Mean (SD)	18.35 (4.633)	17.71 (4.304)	0.64 (0.478)	0.181 ^a
Week 26	n=185	n=191		
Mean (SD)	18.20 (4.509)	16.99 (4.130)	1.25 (0.465)	0.008 ^a
Difference, Week 26 minus baseline	n=170	n=181		
Mean (SD)	-0.07 (2.998)	-0.68 (3.216)	0.78 (0.308)	0.012 ^b
Median	0.00	-0.25		

ANCOVA=analysis of covariance; ANOVA=analysis of variance; ITT=intent-to-treat; LS=least squares; SD=standard deviation; SE=standard error; VAT=ventilatory anaerobic threshold; VO₂=minute oxygen consumption

a P-value was assessed using ANOVA with fixed factors for ventricular morphology (single left versus single right or mixed) and treatment group.

b P-value was assessed using ANCOVA with fixed factors for ventricular morphology (single left versus single right or mixed) and treatment group with a continuous covariate of baseline maximal VO₂.

Source: [Table 14.2.3.1.1](#) and [Table 14.2.4.1.1](#)

Program: [T_14_2_3_1_1.sas](#) and [T_14_2_4_1_1.sas](#)

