11.4.2.2 Handling of Dropouts or Missing Data

The following imputation method was used for the primary analysis of the primary outcome:

- Subjects who died or dropped out of the study with unknown vital status were to be assigned a maximal VO_2 of zero at Week 26. No subject met this criterion.
- Subjects who were known to be alive, but who discontinued from the study (and were missing maximal VO_2 at Week 26) were assigned the latest value available.

- Subjects who completed Week 26 but were physically unable to reach maximum effort in cardiopulmonary exercise testing after 2 attempts, were assigned their baseline value (ie, zero change).

Two additional sensitivity analyses to assess the impact of missing data were conducted as follows:

- Subjects with missing maximal VO₂ at Week 26 were assigned a maximal VO₂ of zero.
- Subjects with missing maximal VO₂ at Week 26 were excluded from analysis (ie, observed cases analysis).

An additional imputation method for missing data was included for exercise variables. When the Week 26 value was missing, the mean of non-missing Week 26 values (ignoring treatment group) was imputed.

For VO₂ at VAT, a linear regression model was used to predict Week 26 VO₂ at VAT from Week 26 maximal VO₂. The predicted value from the model was used to impute VO₂ at VAT when maximal VO₂ was available; when maximal VO₂ was also missing, the average from all subjects with non-missing values was imputed.

Missing item scores for rating scales were imputed according to published methodology for the scale. Otherwise, missing data were not estimated for secondary efficacy endpoints.

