The protocol-specified primary endpoint of maximal VO₂ measures overall aerobic capacity and has been shown to be useful as a predictor of cardiac death and hospitalization for heart failure, both in congenital and acquired heart disease. Given the relative ease of obtaining this measure and its utility as a surrogate outcome, maximal VO₂ has been chosen as an endpoint in multiple observational studies and clinical trials. In view of the above, and to be consistent with generally accepted understanding in the pediatric cardiology community, maximal VO₂ was chosen as the primary endpoint for the FUEL trial. An alternative exercise measure, VO₂ at VAT, was also considered during the initial study design, but was designated as a secondary endpoint for 2 reasons: 1) There were more limited relevant data from prior studies to allow for a robust power calculation, and 2) VO₂ at VAT is more difficult to measure precisely, which could lead to data loss and impact statistical power in this rare pediatric disease. The concern about data loss was confirmed in the FUEL trial in which 21% of participants did not have paired data VO₂ at VAT ([Table 14.2.3.1.2](#)) versus 5% for maximal VO₂ ([Table 14.2.1.1.2](#)).

Despite its utility in most forms of heart disease, recent publications suggest that maximal VO₂ may not be an ideal efficacy measure for interventions in Fontan physiology, particularly for therapies that would improve exercise performance by modification of the PVR. During

exercise, there is a substantial increase in metabolic demand for oxygen delivery and, therefore, cardiac output. In the absence of a sub-pulmonary pump, preload is maintained by the pressure gradient across the pulmonary vascular bed; the difference between CVP and atrial pressure. As exercise intensity increases, CVP must rise to allow for increased transpulmonary blood flow (Qp). Udenafil may modulate this relationship by lowering PVR and therefore allowing for a lower CVP for any given amount of Qp. However, as exercise intensity increases, modification of PVR alone may not be sufficient to allow for the needed increase in cardiac output. Even with optimal pulmonary vasodilation, an increase in CVP is required to provide adequate Qp to keep up with metabolic demand. At the highest levels of exertion, one begins to exceed the physiologic limit of maximal CVP. This physiologic limit, or ceiling, is that point at which exercise is limited by an inability to raise CVP any further.

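### The VAT and other secondary exercise results are headlined with LOCF, although the SAP and the report both say missing secondary data are not estimated, and 9.8.2 does not list the departure

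*SAP*

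**What the plan says.** The document filed as the protocol is a clinical study report, called the report here.

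- **Rule.** SAP 6.4.3 introduces its last-value and zero assignments with "The following imputation method will be used for the primary analysis of the primary outcome". After the rating-scale exception it closes: "Otherwise, missing data will not be estimated for secondary efficacy endpoints".
- **Rule repeated.** Report 9.7.1.4.4 says the same. Report 11.4.2.2 adds two further methods for exercise variables (the Week 26 mean, and a regression for VO2 at VAT) and then states: "Otherwise, missing data were not estimated for secondary efficacy endpoints". LOCF for secondary endpoints is not among the exceptions.
- **Endpoint status.** VO2 at VAT, VE/VCO2 at VAT, work rate at VAT, and respiratory rate, minute ventilation and work rate at peak are secondary in SAP 6.4.2. Report 9.5.2 says VO2 at VAT "was chosen as a secondary exercise measure due to the technical challenge" of measuring it.
- **What was reported.** The titles of Tables 15, 17 and 18 carry the words "Using Last Observation Carried Forward (ITT Population"). Section 11.4.1.3 gives the treatment difference as VO2 at "VAT was 41.58 mL/min (p=0.023"). The LOCF figures are the ones carried into 11.4.1.1, 11.4.1.4, 11.4.7 and 13.
- **Declared changes.** Report 9.8.2.1 to 9.8.2.4 list the mean and regression imputations and mention minor clarifications. They do not list LOCF for secondary endpoints. Section 9.8.2.3 does list mL/min as added after the blind was broken.

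**The concern.** After the primary endpoint missed significance (p=0.071), report 11.4.1 says the efficacy summary will concentrate on measures at VAT. Those estimates should follow the SAP's missing-data rule or be declared as departures. They do neither, and 11.4.2.2 tells the reader the opposite of what the tables show.

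A carried-forward baseline asserts exactly no change. That pulls each arm's mean change toward zero and shrinks its SD, so it alters the estimate, the standard error and the p-value. The table rows print 170 and 181 subjects for the VO2 at VAT change, but not how many of those changes were imputed.

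Handling also varies within the secondary endpoints. Table 19 (MPI) states that nothing was imputed. Figures 4 and 5 are titled LOCF but carry a no-imputation note. A reader cannot tell which rule applied.

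**Working it through.** **Inputs, VO2 at VAT in mL/min** (report Tables 12 and 15; mean change with SD)

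| | LOCF | Observed cases |
|---|---|---|
| Udenafil | "29.65 (177.023"), n=170 | 32.52 (185.191), n not printed |
| Placebo | -8.01 (183.031), n=181 | -8.95 (193.508), n not printed |
| LS mean difference (SE) | 41.58 (18.224) | 50.56 (20.074) |
| Printed p | 0.023 | 0.012 |

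**1. Reproduce the printed p-values.** t = difference / SE, two-sided, df = n − 4 (intercept, treatment, morphology, baseline).
- LOCF: 41.58/18.224 = 2.28, df 347, p=0.023. The 95% CI is about 5.7 to 77.4.
- Observed cases, using n=317 from step 2: 50.56/20.074 = 2.52, df 313, p=0.012. The 95% CI is about 11.1 to 90.1.

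**2. Recover the paired counts.** If every carried-forward value is a baseline value, its change is zero, so observed n = LOCF n × LOCF mean / observed mean.
- Udenafil: 170 × 29.65/32.52 = 155.0 (rounding range 154.95 to 155.05).
- Placebo: 181 × 8.01/8.95 = 162.0 (161.80 to 162.18).

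**3. Check the zeros against the SDs.** Rebuild the LOCF SD from the observed changes plus zeros.
- Udenafil, 155 observed + 15 zeros: mean 155 × 32.52/170 = 29.65. SD = √[(154 × 185.191² + 155 × 32.52² − 170 × 29.65²)/169] = 177.02. Printed: 177.023.
- Placebo, 162 observed + 19 zeros: mean 162 × (−8.95)/181 = −8.01. SD = √[(161 × 193.508² + 162 × 8.95² − 181 × 8.01²)/180] = 183.03. Printed: 183.031.

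One subject more or fewer moves the SD by more than 0.5, so the counts are fixed.

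**4. Cross-check.** 155 + 162 = 317 pairs, and 83/400 = 20.75% are unpaired. Report 11.4.7 says "21% of participants did not have paired data". Of the 83, (200 − 170) + (200 − 181) = 49 lack a baseline value and are in neither analysis; 15 + 19 = 34 lack a Week 26 value and are imputed under LOCF.

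**5. How many of the 34 had no usable Week 26 test at all?** The step 2 formula applied to maximal VO2 (Table 12) gives 200 × 44.40/46.98 = 189 udenafil pairs and 200 × 3.65/3.84 = 190 placebo pairs. So 21 subjects lack Week 26 maximal VO2 (5.25%, agreeing with the 5% in 11.4.7). At most 21 of the 34 can come from that group, so at least 13 had a Week 26 maximal VO2 but no VAT value. The documents do not give the split.

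**6. Effect of following the SAP's missing-data rule** (report 11.4.1.3 and 11.4.1.4.1)

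| Change from baseline | LOCF | No imputation |
|---|---|---|
| VO2 at VAT, mL/kg/min | 0.78, p=0.012 | p=0.009 (estimate not printed) |
| VO2 at VAT, mL/min (post hoc unit) | 41.58, p=0.023 | 50.56, p=0.012 |
| Work rate at VAT | p=0.029 | p=0.021 |
| VE/VCO2 at VAT | p=0.011 | p=0.014 |

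For the SAP-listed peak endpoints the report text gives only LOCF p-values: respiratory rate 0.696, minute ventilation 0.915, work rate 0.891.

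**The case against.** **The departure is visible.** The table titles say LOCF, Table 15 prints its row counts, Table 12 sets the observed-case estimate beside the LOCF one, and the text gives the no-imputation p-values. This stands: nothing is concealed. But a title does not reconcile 11.4.2.2 with the tables or replace an entry in 9.8.2. The reference in 9.8.2.3 to an additional method might suggest LOCF was already in place for all exercise variables, but SAP 6.4.3 confines it to the primary outcome.

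**A reader might infer that LOCF understates the effect by about 18%** ((50.56 − 41.58)/50.56). The documents do not support that. The observed-case estimate rests on its own missing-data assumption and is not the truth. The gap of 8.98 mL/min is about 0.45 of its SE, and the intervals overlap heavily. Both figures are in a unit added after unblinding, and no observed-case estimate is printed in mL/kg/min.

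**A reader might infer that all 34 imputed values reflect difficulty in measuring VAT.** Step 5 shows that up to 21 may be subjects with no usable Week 26 test.

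**Scope.** Several Table 18 rows are outside the SAP's secondary list: VE/VCO2, heart rate and respiratory exchange ratio at peak. Its minute VO2 row is the primary variable in other units. The point does not cover those rows.

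**No conclusion changes.** Correct for the headline change-from-baseline results. The percent-change version of work rate at VAT does move from 0.053 to 0.035, but SAP 6.4.2 specifies change, not percent change.

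**Conclusion.** The point holds as an undeclared departure from the SAP's missing-data rule in the endpoints on which the report leans most. For VO2 at VAT, 34 of the 351 changes analysed are imputed zeros. Following the rule moves p from 0.012 to 0.009 in mL/kg/min, and the mL/min estimate from 41.58 to 50.56. Work rate at VAT strengthens slightly and VE/VCO2 at VAT weakens slightly. No headline VAT result crosses 0.05, and SAP 6.4.5 makes all these p-values nominal.

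The counts are derived, not printed, but they match both means and both SDs. A reader might infer that LOCF was chosen to flatter udenafil; for VO2 and work rate at VAT it worked the other way.

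The no-imputation figures follow the plan on missing data only. The footnotes to Tables 12 and 15 name baseline maximal VO2 as covariate, whereas SAP 6.4.2 asks for the endpoint's own baseline. That mismatch needs separate resolution, so 50.56 should not be called the planned result without qualification.

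**What to change.** - Make the no-imputation tables the main results for the SAP-listed secondary exercise endpoints: 14.2.4.1.2 (VO2 at VAT in mL/kg/min, leading), 14.2.3.1.2 (mL/min, labelled post hoc), 14.2.13.1.2 and 14.2.14.1.2, and for the peak endpoints 14.2.7.1.2, 14.2.8.1.2 and 14.2.9.1.2.
- State paired and imputed counts by arm in tables and text, and how many imputed subjects had no usable Week 26 test.
- Keep LOCF as a labelled sensitivity analysis and list it in 9.8.2 as a departure from the SAP.
- Reconcile 9.7.1.4.4 and 11.4.2.2 with the tables, correct the titles or notes of Figures 4 and 5, and carry the changes through 11.4.1, 11.4.7 and 13.
- Describe all these p-values as nominal.

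The cost is small, because the tables already exist; the work is substitution and text editing. VE/VCO2 at VAT becomes slightly less favourable. The larger mL/min estimate moves into view, which is why its post hoc label matters.
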